4.7 Dispensing and Return of the OraQuick® HIV Self-Test Device

One OraQuick® Rapid HIV Self-Test will be provided to each participant who qualifies for self-testing. At the conclusion of all testing, the used devices will be collected by the study staff and discarded in accordance with local requirements at the site.

4.8 Participant Self Testing

Study participants will be instructed to perform the self-testing using the OraQuick® Rapid HIV Self-Test. The self-testing is to be completed under the direct observation of the study staff. The study staff will verbally instruct the participant as follows:

"This is the part of the study in which you will be asked to use the study product. With this product and the instructions provided, you can perform the test yourself. Although I will be in the room observing you, I will not be able to answer any questions or talk to you while you are using the product, but I will be looking to see how you use it. When you are finished, I would like you to tell me what you think the

CONFIDENTIAL Page 18 of 45

test result is. I will also ask you questions about your experience and what you observed during the test."

Version 1: 13-Jul-2021

The participant will then be permitted to perform the self-test. Their test result and any additional comments will be record in Appendix D - Participant's OraQuick® HIV Self-Test Result Record Form. After the result interpretation portion, the Observer will ask the participant questions about the test procedure and complete Appendix F - Self-Test Questionnaire with the participant's responses.

4.9 Observations and Verification of Participant Self-Testing

The self-testing site must minimally provide for the following:

- Privacy from other study participants, or study staff other than the staff performing observations
- Seating
- Counter, desk, or other space to place the test kit
- Adequate lighting, with the ability for the participant to control lighting
- An obvious manner to measure time (wall clock, desk clock)

Dependent upon the study sites' physical layout, the research staff observing the study participant may or may not be visible to the participant. In any case, the staff is **not** to interact with the participant during testing, unless intervention is required for a study participants' wellbeing or privacy. During the study participant self-testing, the study staff will collect the following observational data for correct performance of the test. These ratings will be collected as the Observational Ratings of Self-Test Performance. Data that will be collected are described in Appendix E - Observer's data collection form.

Observational Ratings of Study Participant-Self Test Performance include:

- Did the study participant read the instructions for use?
- Was the study participant able to find the test tube packet?
- Did the study participant remove the test tube from the packet?
- Did the study participant remove the cap from the test tube?
- Did the study participant place the test tube in the holder?
- Did the study participant have any difficulty with the test tube?
- Was the study participant able to find the test stick packet?
- Did the study participant remove the test stick from the packet?
- Did the study participant touch the flat pad?
- Did the study participant collect the sample correctly (1x upper and lower swab)?
- Did the study participant place the test stick in the test tube correctly?

Observers will also record the following:

CONFIDENTIAL Page 19 of 45

• IFU language instruction the study participant used (French or English)

Version 1: 13-Jul-2021

- Time study participant starts the test (places the device in the test stand after collecting oral fluid).
- Time of study participant reads the test.
- Study participant's apparent level of distress:
 - o Calm
 - Appears anxious
 - Verbally communicates distress
 - Staff intervention required

After the study participant has completed the self-testing they will be requested to provide their result to the staff. The Observer will question the study participant, as follows:

"According to the product instructions, can you please tell me what you think the result of your test is?"

Any ambiguous verbal answer by the participant will have one attempt made to clarify it.

The study participant's response will be interpreted by a check box with five possible selections:

- Do not have HIV / negative
- May have HIV / preliminary positive
- Test not working / invalid
- Not sure / don't know
- Refused or ambiguous answer

If the test could not be completed, this will also be documented.

The Observer will also review the study participant's interpretation of their test.

4.10 Observer's Interpretation of Study Participant's Self-Test Result

Following the completion of the study participant's self-testing interpretation, the Observer will make their own interpretation of the study participant's test result. This should be the site staff who observed the study participant's self-test. Data to be collected will be:

• The Observer's interpretation of the study participant's self-test result.

The Observer's interpretation of the study participant's self-test is intended to allow for review of the data regarding study participants' potential failure to obtain a result versus incorrect interpretation of the result they do obtain.

In the case of a truly invalid test by the study participant, the test will not be repeated.

CONFIDENTIAL Page 20 of 45

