3. STUDY DESIGN

3.1. Overall Study Design

[figure not shown]
This is a cross-sectional study that employs both observational and interview-based methods.

A minimum of 900 lay participants (non-healthcare professional and inexperienced in HIV self-testing) will read the instructions for use (IFU) and conduct the OraQuick® HIV Self-Test. They will not be provided any training prior to use of the test. A trained healthcare provider or researcher (trained Observer) will watch, and document use of the test and independently read the participants self-test result. The participants will then complete a questionnaire to share their opinion on usability and label comprehension of this test. A minimum of 400 participants will also be provided five mock devices with different results and asked to interpret those results i.e. strong positive; weak positive, negative, invalid with no control and no test line, and invalid with no control and a positive test line.¹⁴

All participants will also have a venous blood sample collected for testing of plasma at a central laboratory with a 4th generation HIV enzyme immunoassay (EIA) that will serve as the Comparator Method (CM). All self-tests will be confirmed using a Canadian standard HIV testing algorithm. The sensitivity and specificity of the self-test result will be calculated relative to the "clinical truth" of the participants' HIV status determined by the confirmatory test process, where applicable. Participants will be instructed to return to the clinic for a follow-up visit, two (2) weeks after self-testing to obtain their laboratory test results which will be their official result.

CONFIDENTIAL Page 10 of 45

Flowchart representation of the overall process from recruitment through Confirmatory testing:

CONFIDENTIAL Page 11 of 45

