3.4. Study Description

Usability

The self-test portion of the study will be performed on consenting persons (referred to as participants) and will include recruitment of participants who have consented to be tested for HIV as per the test procedures outlined.

The participant will be evaluated for the self-test process success or difficulty by a silent, non-interacting trained healthcare professional / researcher (Observer) in the same room. Overall processes include self-test Usability (observation to determine if participants perform all critical steps correctly), Results Interpretation (confirmation by observer to determine if participant interprets test results correctly), and Label Comprehension (questionnaire to determine that the participant is aware of test limitations and what to do following the test result). Successful completion of these tasks will be evaluated as a percentage of the overall process, with all critical errors identified.

Each participant will obtain an oral fluid specimen and perform the test, including result interpretation, according to only those materials provided with the OraQuick® HIV Self-Test (e.g. instructions for use).

Each self-test will be observed by trained healthcare professional/ researcher (referred to as Observers). The Observer does not tutor or interact with the participant conducting the self-test but notes errors and other observations about the participant.

CONFIDENTIAL Page 12 of 45

The Observer also interprets the test result, immediately after the participant and within the validated reading time stated in the instructions for use and records the result separately.

Version 1: 13-Jul-2021

All participants will have a venous blood sample taken (typically from the forearm; up to 7mls or about 1.5 tablespoons) and sent to a local provincial laboratory for HIV EIA testing. The laboratory portion of the study will conduct Comparator Method ("CM") testing on plasma from venous blood samples collected from study participants with Health Canada licensed HIV-1/HIV-2 combination antigen/antibody test that is in routine use in the participating local laboratories. Results of all laboratory testing will be shared with the intended use sites since the lab test will serve as the standard of care test.

Sites will be using their local lab or arrange to have samples sent to a lab that uses the same comparator assay.

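### Section 3.1 calls the Observer's reading independent, but the Observer asks for the participant's answer first, so the descriptive own-device comparison is unmasked

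*Combined protocol and SAP*

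**What the plan says.** All references are to the combined protocol and SAP.

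- **3.1** says that the trained Observer will watch the test and "independently read the participants self-test result".
- **3.4** gives that reading its role, which is "confirmation by observer to determine if participant interprets test results correctly". It places the reading "immediately after the participant and within the validated reading time stated in the instructions for use and records the result separately".
- **4.9** has the Observer put the question to the participant: "can you please tell me what you think the result of your test is". It adds: "Any ambiguous verbal answer by the participant will have one attempt made to clarify it". The participant's "response will be interpreted by a check box with five possible selections". The section ends with a sentence that begins "The Observer will also review the study" and goes on to the participant's interpretation.
- **4.10** sets the Observer's reading after the participant's "self-testing interpretation, the Observer will make their own interpretation of the study" participant's result. It says that the reader should be the staff member who observed that self-test. It gives the purpose as telling apart participants who never got a result from those who misread the one they had.
- **6.4** lists the Observer's interpretation among additional secondary items, for descriptive statistics only.
- **6.3** bases primary sensitivity and specificity on the participant's own reading against laboratory status.

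**The concern.** A second reading is a fair check on the first only if the second reader does not know the first answer. Here the Observer has asked for the answer and heard it before reading the strip. With a faint line, or a strip that may be invalid, a reader who has just heard an answer may be drawn towards it. Any such pull runs one way: a misreading is recorded as agreement.

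Two results depend on this reading. One is the comparison of participant and Observer on the participant's own device. The other is the 4.10 split between not getting a result and misreading it; if the Observer follows a misreading, the error is put down to the device or the procedure instead of to interpretation. The word *independently* in 3.1 would also let a report claim a property that the described procedure does not secure.

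**Working it through.** The plan gives no agreement target, misreading rate or sample-size figure for this comparison, so there is nothing to reproduce. The check is first on the text.

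**1. Order of events**

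| Step | Section | Status in the text |
|---|---|---|
| Participant reads the device | 3.4, 4.8 | Explicit |
| Observer asks for the answer | 4.9 | Explicit |
| One clarification if ambiguous | 4.9 | Explicit, but passive; that the Observer does it is inferred |
| Observer reviews the participant's interpretation | 4.9 | Explicit; that it precedes the Observer's own reading is inferred from section order |
| Same Observer makes own reading | 3.4, 4.10 | Explicit, and after the participant's interpretation |
| Observer's reading recorded separately | 3.4 | Explicit; keeps the record apart but does not hide the answer |

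The point rests on the explicit steps alone. No section describes an Observer reading locked before the answer is known, or a second reader unaware of it.

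**2. What the reading can and cannot change**

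- *HIV-positive participant, positive strip, read as negative.* In 6.3 this is a false negative whatever the Observer records. Only its explanation depends on the Observer.
- *HIV-negative participant, invalid strip, read as negative.* In 6.3 this is a true negative, because the participant's answer agrees with the laboratory. Only the Observer's reading could reveal the error. Section 4.7 has used devices collected and discarded, and no photograph or later re-reading is described.
- *Mock devices (4.11).* The result types are set by the manufacturer, so the Observer's reading of the participant's own strip plays no part in the 400 × 5 = 2,000 readings.

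**3. Illustration of scale (rates assumed)**

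From the protocol: n = 900. Assumed: m, the share of participants who misread their strip, and a, the share of those misreadings that the Observer follows. The Observer is taken to read correctly otherwise.

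- Misreadings recorded as agreement = 900 × m × a
- Rise in agreement = m × a
- Misreadings still recorded = 900 × m × (1 − a), so the count is understated by the share a whatever m is

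| m (misreadings) | a = 10% | a = 25% | a = 50% |
|---|---|---|---|
| 1% (9) | 0.9; +0.10 points | 2.25; +0.25 | 4.5; +0.50 |
| 2% (18) | 1.8; +0.20 | 4.5; +0.50 | 9; +1.00 |
| 5% (45) | 4.5; +0.50 | 11.25; +1.25 | 22.5; +2.50 |

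Each cell gives the expected number recorded as agreement, then the rise in agreement in percentage points. At m = 2% and a = 50%, agreement goes from 882/900 = 98% to 891/900 = 99%.

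**The case against.** *Independently* may mean only without consultation. Section 3.4 openly puts the Observer second and asks for a separate record, and 3.1 never says masked. That softens the conflict of wording, but the reader still knows the answer.

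The pull towards the participant's answer is assumed, not shown. The Observer is in the room and may have seen the strip and formed a view before the answer is given. Appendices D and E are not reproduced, so a form might set an entry order. Both points stand: the bias is possible, not established. The randomized order of the mock devices is no counter-example, since it deals with sequence effects and not with reader masking.

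The consequence is small, because the item is descriptive and has no threshold. That also stands, and it sets the severity.

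The strongest objection is to the remedy. The spoken answer also supplies the 6.3 variable. If clarification comes after the Observer has read the strip, whoever clarifies may know what it showed. This is a real risk. It is why the change should leave the five-category check box alone, preserve the participant's recorded answer, fix the clarification wording and count the clarifications. Those steps make any influence visible but do not remove it.

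**Conclusion.** The point holds as a minor one, with medium confidence. The Observer's reading is unmasked on the visible text. The own-device comparison in 3.4 and 6.4, and the split in 4.10, may therefore be biased towards agreement. The amount cannot be derived; the table above shows scale under assumed rates and says nothing about what this trial will find.

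A reader might infer more than the documents support:

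- *That primary accuracy is biased.* Section 6.3 scores the participant's own reading, so the Observer's reading does not enter it. This takes the invalid results excluded there to be the participant's own calls, in line with that section's opening sentence.
- *That the laboratory comparison catches every misreading anyway.* It does not catch an invalid strip read as negative by an HIV-negative participant, which is what gives the Observer's reading its separate value.
- *That the Observer certainly clarifies and reviews the answer before reading.* Both are inferences, and the point does not need them.
- *That 3.1 promises blinding.* It promises independence, which the described order does not secure.

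**What to change.** Keep the participant reading first and change the order in 4.8–4.10:

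1. The participant finishes reading and fixes their answer on Appendix D, out of the Observer's view.
2. The Observer reads the device within the validated window, then enters and locks that reading without disclosing it, before seeing or hearing the answer.
3. Only then is the 4.9 question asked and the existing five-category check box completed.

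Keep the participant's first recorded answer unchanged alongside any clarified one. Use fixed neutral wording for the single clarification, and report how many answers were clarified. Where a participant cannot write, keep the spoken answer and flag the Observer's reading as unmasked. Report the participant-by-Observer cross-table with and without flagged readings. Align *independently* in 3.1 and the review sentence in 4.9 with this order. No change to the counselling in 4.14–4.15 is proposed.

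**Cost.** No extra reader, visit or sample is needed, but there is a form and training change and one short entry per participant. At an assumed 0.5, 1 or 2 minutes, 900 entries take 450, 900 or 1,800 minutes (7.5, 15 or 30 hours), or about 1.1, 2.1 or 4.3 hours per site at seven sites. If 1%, 5% or 10% cannot write (assumed), 9, 45 or 90 readings are flagged. The out-of-view entry must be fitted to the direct observation required in 4.8. It could push the Observer past minute 40 of the window in 6.6 when the participant reads late, although the current order already puts a spoken answer first. Masking stays partial, since the Observer also rates apparent distress.

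**If the order is not changed,** drop *independently* from 3.1 and report the Observer's reading as unmasked.

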4.11 Interpretation of Results – Mock Devices

At the end of the self-testing process, the Observer may ask subjects to participate in a 'Mock Result Interpretation' study that will involve interpreting a separate set of OraQuick® HIV Self-Test results prepared by the manufacturer. Participation is voluntary and up to 400 participants recruited from the 900 participants who consented for the device accuracy study will conduct this Mock Result Interpretation. If participant agrees to participate, they will be presented with five (5) OraQuick® HIV Self-Test mock result types and asked to interpret the results using the Self-Test instructions for use (IFU) as a guide. The five (5) mock devices will be the following:

Version 1: 13-Jul-2021

- 1. Strong Positive
- 2. Weak Positive
- 3. Negative
- 4. Invalid (no control line present, test line present)
- 5. Invalid (no control line or test line present)

Mock devices will be presented in a randomized order to control bias.

Although the self-test study participants will be interpreting the results of their own OraQuick® HIV Self-Test, the purpose of this sub-study is to document if intended users, (non-professional and inexperienced in HIV self-testing), can successfully interpret contrived/mock strong positive, weak positive, negative and invalid results. Results of this interpretation will be recorded by the Observer on Appendix G - Participant's Mock OraQuick® HIV Self-Test Result Interpretation Record Form.

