2. STUDY OBJECTIVES

The primary objectives of this study will be to:

- 1) Evaluate the device performance, i.e. sensitivity and specificity, compared to laboratory reference testing
- 2) To document if intended users (non-professional "lay users"), can successfully perform the steps to use the OraQuick® HIV Self-Test, without product familiarization or demonstration (accuracy/usability)
- 3) To document if intended users, (non-professional "lay users"), can successfully interpret contrived strong positive, weak positive, negative, and a range of invalid results (test results interpretation) and
- 4) To document if intended users can understand the key messages in the labeling (label comprehension).

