4. STUDY PROCEDURES

4.1 Recruitment

Participants will be recruited from up to seven (7) geographically distinct Canadian sites. Prospective participants will be representative of the Canadian HIV testing population, including a minimum of 400 participants at risk for HIV infection (e.g. IDU, MSM, etc.).

Version 1: 13-Jul-2021

Recruitment of participants will be done through i) clinic and community-based recruitment - after strategic planning and relevant research, the co-investigators will identify active HIV testing clinics and institutions that have an appropriate participant base, ii) word-of-mouth recruitment - participants will be encouraged to tell others about the study and iii) various media channels.

Once participants have been identified through recruitment, they will be approached, informed about the study and the role they will play in the study procedure. These participants must consent to be tested for HIV as per the study site's standard of care procedures before enrolling in the study. These sites will direct all investigative and administrative functions for the study. The participating sites must have the ability to comply with all local government requirements for HIV testing and reporting.

It is anticipated that the target population for this study will include a mix of highrisk and low-risk populations. The total study population will include a minimum of 900 participants whose HIV status is unknown. All 900 participants will be assessed for usability and label comprehension and 400 from the 900 participants enrolled will be asked to participate in a results interpretation study using premade devices that will mimic the different test results that might be observed.

Study numbers for each of the study objectives were not computed. They were determined to meet compliance requirements from the Health Canada Guidance Document: Guidance for Manufacturers pf Human Immunodeficiency Virus (HIV) Rapid Diagnostic Tests (RDTs) for use at the point of Care of for Self-Testing.¹⁴

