6.7. Sample Size

Sample size for this study was based on the Health Canada Guidance Document: Guidance for Manufacturers of Human Immunodeficiency Virus (HIV) Rapid Diagnostic Tests (RDTs) for use at the Point of Care or for Self-Testing. ¹⁴ The sample size requirements for a near-patient study with untrained self-testers is a minimum of 900 laypersons with unknown HIV status, including 400 persons at risk for HIV infection (e.g. IDU, MSM, etc.). To assess the ability of untrained self-testers to correctly interpret a variety of pre-made mock (contrived) devices test results, a minimum of 400 persons are required. A minimum of 200 self-testers are required to assess for label comprehension. ¹⁴

CONFIDENTIAL Page 26 of 45

It should be noted that the OraQuick ADVANCE® HIV-1/2 Rapid Antigen Test is not intended for use by individuals that are known to be HIV positive.

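### The mock-device reading for primary objective 3 has 400 as a floor in 3.1 and 6.7 but as a ceiling in 4.11, and no visible rule says whom the Observer invites

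*Combined protocol and SAP*

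**What the plan says.** Objective 3 in section 2, listed as primary, is to document whether lay users can read contrived positive, negative and invalid results. Four places in the combined protocol and SAP bear on how many people do this:

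- Section 3.1: "A minimum of 400 participants will also be provided five mock devices with different results".
- Section 6.7: for the mock reading, "a minimum of 400 persons are required".
- Section 4.1: "400 from the 900 participants enrolled will be asked to participate in a results interpretation study".
- Section 4.11: "Participation is voluntary and up to 400 participants recruited from the 900 participants".

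Section 4.1 adds that the study numbers were not calculated but taken from the Health Canada guidance. Section 6.4 lists the mock results among descriptive secondary analyses, and the visible text sets no pass threshold.

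On who is invited, 4.11 says "At the end of the self-testing process, the Observer may ask subjects to participate". By that point the steps of the self-test have been rated (4.9), the participant has stated a result, and "The Observer will also review the study participant's interpretation of their test". Section 4.10 then has the Observer read the same device: "This should be the site staff who observed the study participant's self-test". Section 4.11 randomises the order of the mock devices. It does not say how participants are chosen.

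**The concern.** There are two separate matters.

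The first is the number. A site that follows 4.11 to the letter may stop at or below 400 and still comply with its procedure, while the study falls short of 6.7. Because the 400 rests on no power or precision calculation, meeting it is the whole of its justification. A shortfall would be a failure against the plan's own figure for a primary objective.

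The second is the choice of invitees. About 400 of 900 are to read the mock devices, and the invitation is at the discretion of an Observer who may just have seen how well the person tested and read a result. With no threshold, the percentage read correctly is itself the evidence for objective 3. It should not depend on who was thought worth asking.

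**Working it through.** **The plan's own figure.** No formula can reproduce the 400, since 4.1 says it was not computed. It can only be compared across sections.

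**Consistency.** Let R be the number of completed mock readings. Sections 3.1 and 6.7 require R ≥ 400. Section 4.11 requires R ≤ 400. Both hold only at R = 400. Section 4.1 fixes the number asked, A = 400, and does not fix R.

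**If 4.1 limits invitations.** Participation is voluntary, so let u be uptake. The documents give no value for u; those below are assumed. Expected readers are 400u, and the chance that all 400 agree is u^400 (taking decisions as independent). To reach 400 readers on average takes 400/u invitations, rounded up. The last column is the smallest number of invitations giving at least a 95% binomial chance of 400 readers.

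| Assumed uptake | Readers if 400 asked | Invitations for 400 on average | Invitations for 95% chance of 400 |
|---|---|---|---|
| 99% | 396 | 405 | 408 |
| 95% | 380 | 422 | 429 |
| 90% | 360 | 445 | 456 |
| 80% | 320 | 500 | 519 |
| 70% | 280 | 572 | 598 |
| 50% | 200 | 800 | 847 |

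Even at 99% uptake the chance that all 400 agree is 0.99^400 = 1.8%. Every invitation count in the table is within the 900 enrolled.

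**Precision.** At 95% read correctly, the Wilson 95% limits are 92.4% to 96.7% for 380/400, 92.2% to 96.8% for 342/360 and 92.0% to 96.9% for 304/320. The loss is negligible.

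**Selection, as one hypothetical illustration.** None of these inputs comes from the documents. Suppose 10% of participants read the weak positive correctly 80% of the time and the rest 95%. The true figure is 0.10 × 0.80 + 0.90 × 0.95 = 93.5%. Let k be the weaker group's chance of being asked relative to the others. Their share among those asked is q = 0.10k / (0.10k + 0.90), and the result is 0.80q + 0.95(1 − q).

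- k = 0 (never asked): q = 0, result 95.0%, up 1.5 points.
- k = 0.5: q = 0.053, up 0.7 points.
- k = 1: no change.
- k = 2: q = 0.182, down 1.2 points.

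For scale, the Wilson half-width at 374/400 (93.5%) is 2.4 points. The result is also unchanged if self-test performance does not predict mock reading.

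**The case against.** On size, the best defence is that this is a wording repair. Section 6.7 is the sample-size section and states a minimum, which 3.1 repeats. Section 4.11 limits how many do the reading, not how many are invited, so staff can keep asking until 400 have read, and exactly 400 satisfies 3.1, 4.11 and 6.7 together. The sentence in 4.1 does not say that only 400 may be asked, and its context is planned totals per task. All of this stands. A reader might infer from the table that the sub-study will miss its minimum. The documents do not support that: the shortfall needs both the limiting reading of 4.1 and an assumed uptake. What remains is that the operating section states a ceiling where the sample-size section states a floor.

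On selection, the permissive wording in 4.11 is ordinary for an optional sub-study. Nothing suggests that Observers have a reason to favour able participants. Known positives are excluded, so a participant's own device need not reveal how they would read a weak positive or an invalid. Section 5.2 gives each site at least two Observers, and 4.11 does not say that the one who invites is the one who watched, although that is the natural reading. The 3.1 flowchart, the consent pages, the content of the appendix forms and the study procedures mentioned in section 5 are not visible, and any of them may hold a rule. This stands too. It shows that bias is unproven; it does not supply a rule.

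Sections 3.4 and 4.12 mention the mock reading without naming the subset. That is loose wording, not a further contradiction.

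**Conclusion.** The number is inconsistent and should be reconciled, because 400 is the only size the plan gives for objective 3. The conflict follows from the text alone and needs no assumption. Any actual shortfall (380 readers at 95% uptake, 320 at 80%) is conditional on 4.1 limiting invitations and on those assumed uptakes. What is at stake is compliance with the stated minimum, not precision.

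The invitation is left to discretion after performance has been seen, and no visible section constrains it. A reader might infer that the mock results will look better than they should. The documents do not show that: in the illustration the shift can go either way, its largest value of 1.5 points is within the 2.4-point half-width, and all its inputs are hypothetical. The supported conclusion is that selection on performance is possible and cheap to rule out. The change is worth making; confidence is moderate because relevant material is not shown.

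**What to change.** In 4.11 replace the ceiling, and in 4.1 replace the number to be asked, with one statement: at least 400 participants will complete the mock reading, with invitations going beyond 400 as needed among the 900 enrolled.

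In 4.11 replace the Observer's discretion with an invitation rule fixed in advance and independent of observed self-test performance. Two examples:

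- Every consecutive participant at each site until enough readings are complete. This is simple but draws on earlier enrolees.
- A fixed interval across enrolment at each site, which spreads readers over time. The interval must allow for refusals: inviting every second participant gives 450 invitations from 900, enough on average only if uptake is at least 400/450 = 88.9%.

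Keep participation voluntary, and report the numbers invited, refused and completed.

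The cost is a few sentences, a simple count, and some extra invitations: 445 − 400 = 45 at 90% uptake or 500 − 400 = 100 at 80%. There may also be more mock sessions than the present ceiling allows. The documents do not say how many mock sets the manufacturer supplies, so supply must be checked. Site shares and a comparison of readers with non-readers on self-test errors would be useful but are optional.
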